3.8.2.7 Clinical response in patients with *PIK3CA* mutant status measured in ctDNA

An analysis of ORR, CBR based on local radiology assessments and using RECIST 1.1 criteria; and OS for (i) patients with *PIK3CA* mutant status and (ii) patients with *PIK3CA* non-mutant status as measured in ctDNA at baseline will be conducted using the same analytical conventions as the endpoint where mutation status is defined in tissue.

3.8.2.8 ECOG performance status

The ECOG PS scale ([Table 3-4](#)) will be used to assess physical health of patients, ranging from 0 (most active) to 5 (least active):

Table 3-4 ECOG Performance Scale

Score	Description
0	Fully active, able to carry on all pre-disease performance without restriction
1	Restricted in physically strenuous activity but ambulatory and able to carry out work of a light or sedentary nature, e.g., light house work, office work
2	Ambulatory and capable of all self-care but unable to carry out any work activities. Up and about more than 50% of waking hours
3	Capable of only limited self-care, confined to bed or chair more than 50% of waking hours
4	Completely disabled. Cannot carry on any self-care. Totally confined to bed or chair
5	Dead

The following intervals will be used to group the ECOG PS data over time. Day in columns 2 and 3 is defined as date of ECOG PS assessment date – randomization date + 1. The corresponding Day in column 1 assumes that a patient is treated on the day of randomization; however the definition of Day in columns 2 and 3 still applies if this is not the case, i.e. randomization date is taken as the reference for the windows.

Table 3-5 Time windows for ECOG PS assessments

Assessment	Target day of assessment	Time Interval
Baseline		Day 1 (if ECOG PS assessment is not available, use the one performed at screening)
Cycle 2 Day 1	29	Day 2 to day 42
Cycle k Day 1 ($k \geq 3$)	$d = (k-1) * 28 + 1$	Day $d-14$ to day $d+13$
End of Treatment		Assessment taken at the end of treatment visit

If 2 assessments within a time window are equidistant from the target date (or if the closest assessment to the target date has two ECOG filled out on the same date), then the worst ECOG PS value will be used.

Time windows are applicable for descriptive summary of ECOG data by visit only. For time to deterioration analysis described hereafter all post-baseline assessments will be considered.

Frequency counts and percentages of patients in each score category will be provided by treatment arm and time point.

Time to definitive deterioration of the ECOG PS is the number of days between the date of randomization and the date of the assessment at which definitive deterioration is seen. The ECOG PS deterioration is considered definitive if there is an increase in the performance status by at least one category relative to the baseline or death due to any cause and if no improvement in ECOG PS is observed subsequent to the deterioration.

Baseline is the last available assessment on or before date of randomization. If a patient has 2 ECOG PS values at the same date, the worst ECOG PS value will be taken as ‘baseline’.

Example: If the ECOG PS is 1 at baseline and then 1, 2, 1, 2, 3 at D28, D57, D83, D115, and D150 respectively, then the time to definitive worsening is D115.

Example: if the ECOG PS is 1 at baseline and then 1, 1, 2 at D28, D57, and D83 respectively, with no assessment of the ECOG PS after D83 then the time to definitive worsening is 83 days.

If a definitive deterioration is observed after any missing assessments, this event will be backdated to the first of the missing assessments before the deterioration. The first missing assessment date is calculated as the last available assessment before the definitive deterioration plus X, where X corresponds to the planned scheduled time point for ECOG PS (28 days).

For example, if a patient has an assessment at week 6, misses the following two assessments on weeks 10 and 14 and a definitive deterioration is observed on week 15, then the event will be backdated to week 6+28 days.

In addition, death is considered as a worsening of performance status if it occurs close to the last available assessment, where “close” is defined as twice the planned (i.e. protocol scheduled) period between two assessments. This avoids overestimating the time to definitive worsening in patients dying after an irregular assessment scheme. Patients who die after more than twice the planned period between two assessments are censored at the date of their last available assessment of the performance status.

For example, if the last assessment is at week 6 and the patient dies at week 10, the definitive deterioration date will be week 10. On the other hand, if the last assessment is at week 6 and the patient dies at week 16, which is after more than twice the planned period between two assessments since the last assessment (week 6), then the definitive deterioration date will be week 6.

Patients receiving any further anti-neoplastic therapy before definitive worsening will be censored at the date of their last assessment before the start date of the therapy. Patients that have not worsened as of the cutoff date will be censored at the date of their last assessment before the cutoff.

Patients without baseline ECOG PS or without any post-baseline ECOG PS will be censored at the date of randomization with censoring reason being ‘No baseline score’ or ‘No post-baseline score’, respectively. However, patients without post-baseline ECOG PS who die within 62 days after date of randomization will be counted as having a definitive deterioration of the ECOG PS at the date of death.

This threshold corresponds to twice the protocol defined ECOG assessment interval plus twice the time window around each assessment: (2 x 28 days)+(2 x 3 days), i.e. 62 days.

Kaplan-Meier estimates will be constructed for each treatment arm in each cohort. The median, 25th and 75th percentiles for time to definitive deterioration for each treatment group will be obtained along with 95% confidence intervals.

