 - If no measurable disease is present, then at least one predominantly lytic bone lesion must be present (patients with no measurable disease and only one predominantly lytic bone lesion that has been previously irradiated are eligible if there is documented evidence of disease progression of the bone lesion after irradiation).
9. Patient has advanced (loco regionally recurrent not amenable to curative therapy or metastatic) breast cancer.
Patients may be:
 - relapsed with documented evidence of progression while on (neo) adjuvant endocrine therapy or within 12 months from completion of (neo)adjuvant endocrine therapy with no treatment for metastatic disease
 - relapsed with documented evidence of progression more than 12 months from completion of (neo)adjuvant endocrine therapy and then subsequently progressed with documented evidence of progression while on or after only one line of endocrine therapy for metastatic disease
 - newly diagnosed advanced breast cancer, then relapsed with documented evidence of progression while on or after only one line of endocrine therapy

Note: i) Patients with newly diagnosed endocrine treatment naïve advanced breast cancer, ii) ii) Patient who relapsed with documented evidence of progression on/or within 12 months from completion of adjuvant endocrine therapy and then subsequently relapsed with documented evidence of progression after one line of endocrine therapy (with either an antiestrogen or an AI) for metastatic disease will NOT be included in the study.

10. Patient has recurrence or progression of disease during or after AI therapy (i.e. letrozole, anastrozole, exemestane). AI therapy does not need to be the latest treatment regimen.
11. Patient has an ECOG performance status 0 or 1

12. Patient has adequate bone marrow and organ function as defined by the following laboratory values (as assessed by central laboratory for eligibility):

- Absolute neutrophil count $\geq 1.5 \times 10^9/L$
- Platelets $\geq 100 \times 10^9/L$
- Hemoglobin $\geq 9.0 \text{ g/dL}$
- Calcium (corrected for serum albumin) and magnesium within normal limits or \leq grade 1 according to NCI-CTCAE version 4.03 if judged clinically not significant by the investigator
- Potassium within normal limits, or corrected with supplements
- International Noramlized Ratio (INR) ≤ 1.5
- Creatinine Clearance $\geq 35 \text{ mL/min}$ using Cockcroft-Gault formula

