10.5.2.6 ECOG Performance Status

ECOG performance status will be used to assess physical health of patients. An analysis of the time to definitive deterioration of the ECOG performance status by one category of the score from baseline will be performed using Kaplan-Meier method. A deterioration is considered definitive if no improvements in the ECOG performance status is observed at a subsequent time of measurement during the treatment period following the time point where the deterioration is observed.

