Time to 10% deterioration in the global health status/ [REDACTED] will be assessed in each cohort. 10% deterioration is defined as a worsening in score by at least 10% compared to baseline, with no later improvement above this threshold observed during the treatment period, or death due to any cause. Time to deterioration is the number of days between the date of randomization and the date of the assessment at which deterioration is seen. If a patient has not had an event prior to analysis cut-off, start of new anti-neoplastic therapy, lost to follow-up, or withdrawal of

consent, the time to deterioration will be censored at the date of the last evaluation before the earliest of these dates. If deterioration is observed after two or more missing assessments, time to deterioration will be censored at the date of the last assessment prior to the deterioration. Patients with no baseline data will be censored at Day 1. Death is considered as an event when it occurs within a period of time defined by 2 times the period between two assessments as planned in the study protocol. This avoids overestimating the time to definitive worsening in patients dying after an irregular assessment scheme. Patients who die after more than twice the planned period between two assessments since the last assessment are censored at the date of their last available questionnaire.

Time to 10% deterioration will be compared between the two treatment arms using a stratified log-rank test (strata based on IRT data) and the survival distributions will be presented descriptively using Kaplan-Meier curves. Summary statistics from the Kaplan-Meier distributions will be determined, including the median time to 10% deterioration and the proportions of patients without 10% deterioration at 6, 12, 18 months. Both point estimates and 95% CIs will be presented. A stratified Cox regression model will be used to estimate the hazard ratio (HR) of time to deterioration, along with 95% confidence interval. Sensitivity analysis of time to definitive deterioration with different cut-off definitions (e.g. 5%, 15%) may also be considered if the number of events per arm is judged sufficient to draw relevant conclusions.

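### ECOG deterioration is triggered against baseline but undone by any later improvement, so a fall of two or more categories with partial recovery can be dated later than a lasting one-category fall

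*SAP*

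**What the plan says.** Time to definitive ECOG deterioration is listed among the other secondary endpoints for both cohorts (Protocol Table 3-1, SAP Table 1-1).

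- **Trigger.** SAP 3.8.2.8 requires an "increase in the performance status by at least one category relative to the baseline", or death.
- **Condition for being definitive.** The same sentence adds "if no improvement in ECOG PS is observed subsequent to the deterioration".
- **Protocol 10.5.2.6.** A deterioration is definitive if "no improvements in the ECOG performance status is observed at a subsequent time of measurement during the treatment period". This wording is equally open about the level but is limited to the treatment period, a limit the SAP sentence does not repeat.
- **Worked examples in SAP 3.8.2.8.** Baseline 1 with scores 1, 2, 1, 2, 3 at D28, D57, D83, D115 and D150: "then the time to definitive worsening is D115". Baseline 1 with scores 1, 1, 2 at D28, D57 and D83: "then the time to definitive worsening is 83 days".
- **Parallel rule.** For the quality-of-life score, SAP 3.8.2.9 defines a lasting 10% worsening as one "with no later improvement above this threshold observed during the treatment period". There the improvement is tied to the deterioration threshold.

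**The concern.** The trigger is anchored to baseline; the condition that undoes it is anchored to nothing. A patient can improve from a very poor score to a moderately poor one, remain worse than baseline throughout, and still have the earlier deterioration set aside. The event then moves to a later visit, and the recorded time becomes longer than that of a patient who lost one category and stayed there. This runs against the section's own reasoning: its rule for deaths is justified by the wish not to overstate the time to definitive worsening.

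What is at stake is the dating, and sometimes the counting, of events in one secondary endpoint, and whether two programmers working from the same text would produce the same dataset.

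**Working it through.** **Inputs.** The trigger, the condition and the two examples are from SAP 3.8.2.8. Baseline is 0 or 1, because the inclusion criterion reads "Patient has an ECOG performance status 0 or 1" (Protocol 5.2). All post-baseline assessments count in this analysis (SAP 3.8.2.8).

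**Three readings of improvement.** Let b be the baseline score. A visit with score x of at least b + 1 is a candidate event. It is set aside if:

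- (a) the score drops between any two later consecutive visits, starting from the candidate visit;
- (b) any later score is better than x;
- (c) any later score is below b + 1.

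Readings (a) and (b) take the words as they stand. Reading (c) supplies the missing threshold.

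**Reproducing the SAP examples.** Example 1 has b = 1, so the threshold is 2. The first candidate is D57 (score 2). The score of 1 at D83 sets it aside under all three readings, and D115 (2, then 3) stands. Example 2: D83 is the first candidate and nothing follows it. All three readings give D115 and D83. The only improvement shown is a full return to baseline, so the examples cannot tell the readings apart.

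**Illustrative sequences.** The scores are assumed; the visit days are those of SAP example 1.

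| Baseline | Scores at D28, D57, D83, D115, D150 | (a) | (b) | (c) |
|---|---|---|---|---|
| 0 | 2, 1, 1, 1, 1 | D57 | D57 | D28 |
| 0 | 1, 2, 1, 1, 1 | D83 | D28 | D28 |
| 1 | 2, 3, 2, 2, 2 | D83 | D28 | D28 |
| 1 | 3, 3, 3, 3, 2 | D150 | D150 | D28 |
| 0 | 1, 1, 2, 2, 3 | D28 | D28 | D28 |
| 1 | 2, 2, 2, 2, 2 | D28 | D28 | D28 |

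The delays against (c) are 57 − 28 = 29 days in the first row, 83 − 28 = 55 days in the second and third under (a) only, and 150 − 28 = 122 days in the fourth.

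**Direction.** Take every five-visit sequence with scores up to 4 that never returns to baseline, so that (c) always gives the first visit.

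- Baseline 0: 4^5 = 1024 sequences. Reading (a) keeps the first visit only if scores never drop, which is 56 sequences, so 1024 − 56 = 968 are dated later. Reading (b) keeps it only if no later score is better than the first, which is 4^4 + 3^4 + 2^4 + 1 = 354, so 1024 − 354 = 670 are later.
- Baseline 1: 3^5 = 243 sequences. Under (a), 243 − 21 = 222 are later. Under (b), 243 − (3^4 + 2^4 + 1) = 243 − 98 = 145 are later.

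No sequence is dated earlier under (a) or (b). These are counts of possible patterns, not expected frequencies.

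**Who can be affected.** The score must go at least two categories above baseline and then partly recover: to 2 or more from baseline 0, or to 3 or more from baseline 1.

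**Lost events.** SAP 3.8.2.8 censors a patient at the last assessment before new anti-neoplastic therapy if that therapy precedes the definitive worsening. Take baseline 0, score 2 at D28, new therapy, then score 1 at D57. Reading (c) gives an event at D28; (a) and (b) give censoring at D28. Scheduled ECOG assessment ends at the end-of-treatment visit (Protocol 7.2.2.4), so the window for this is narrow.

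**The case against.** The best defence is that improvement simply means undoing the increase over baseline named earlier in the same sentence. The only example with an improvement is indeed a return to baseline. The SAP also places further programming details in a separate document that is not available here, and the program may already use the threshold. This stands as a possible intention. It does not supply the missing words: the examples fit every reading, and the next section shows how the qualifier is written when it is meant.

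A reader might also infer more than the documents support:

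- **That everyone who stays worse than baseline is dated later.** Not so. With level or rising scores all readings agree.
- **That each partial recovery costs at least one 28-day cycle.** Not so. Under (b), baseline 0 with 1, 2, 1, 1, 1 is not delayed at all. Nor are assessment gaps fixed at 28 days; the SAP's own example has 83 − 57 = 26 days between two of them.
- **That the treatment comparison is biased.** The rule is the same in both arms, and nothing in the documents shows that partial recovery differs between them.

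**Conclusion.** The concern holds in a limited form. As written, the rule can postpone the event, and occasionally remove it, for patients who worsen by two or more categories and then partly recover while still at least one category worse than baseline. Under the two readings that take the words as they stand, the error goes only towards a later date. The conclusion rests on the wording of the two sections and on illustrative score sequences. How many patients are affected, the average delay and any imbalance between arms cannot be computed from the documents.

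The consequence is small. SAP 3.8.2.8 specifies Kaplan-Meier estimates with the median and quartiles, and gives neither a test nor an alpha level. SAP 4.4.2 speaks generally of log-rank comparisons for secondary endpoints at the levels in Section 3.8, but Section 3.8 assigns none to this one. PFS, OS and the control of type I error are unaffected. This is a desirable correction, not a threat to the trial's conclusions.

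**What to change.** In SAP 3.8.2.8, replace the clause on later improvement with: *and no later ECOG PS is less than one category worse than baseline*. This mirrors the threshold-based rule in SAP 3.8.2.9 and leaves both worked examples at D115 and D83. Adding a third example with a partial recovery, such as baseline 0 with 2, 1, 1, 1 (event at the first visit), would settle the reading.

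The cost is one SAP sentence. Protocol 10.5.2.6 should be aligned when the protocol is next amended, keeping its limit to the treatment period. A protocol change needs a written, approved amendment (Protocol 12.1), and this point does not justify one by itself.

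Protocol Amendment 5 reports that trial results had already supported registration, so output for this endpoint may exist. If it does, the report should state which rule was programmed, and any re-analysis under the clarified rule should be labelled post hoc.

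### SAP 3.8.2.8: the worked example for a late death labels the last ECOG visit as a deterioration date, while the rule it illustrates censors the patient there

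*SAP*

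**What the plan says.** SAP Section 3.8.2.8 measures the endpoint from randomization to "the date of the assessment at which definitive deterioration is seen". Death counts as worsening only if it falls within two planned assessment intervals of the last ECOG, and the section gives the interval as 28 days. For later deaths the rule reads: "Patients who die after more than twice the planned period between two assessments are censored at the date of their last available assessment".

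Two examples follow in one paragraph:

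- Death soon after the last ECOG: "if the last assessment is at week 6 and the patient dies at week 10, the definitive deterioration date will be week 10".
- Death long after it (last ECOG week 6, death week 16, expressly described as beyond the limit): "then the definitive deterioration date will be week 6".

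The section also states that "patients without post-baseline ECOG PS who die within 62 days after date of randomization will be counted as having a definitive deterioration" and that "Patients receiving any further anti-neoplastic therapy before definitive worsening will be censored at the date of their last assessment". Patients who have not worsened by the cut-off are censored at their last assessment before it.

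The parallel rule for questionnaires in SAP Section 3.8.2.9 says that patients who die beyond the same kind of limit "between two assessments since the last assessment are censored at the date of their last available questionnaire". Protocol Section 10.5.2.6 describes the endpoint as "time to definitive deterioration of the ECOG performance status by one category of the score from baseline" and does not mention death.

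**The concern.** The second example contradicts the rule it is meant to illustrate. By the rule the week-16 death is a censored observation. By the example's label it is a deterioration dated at week 6. The immediately preceding sentence uses that label for an undoubted event, and nothing in the section says that it can also mean a censoring date. Where the section means censoring, it says so.

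A literal reading is not far-fetched. The stated purpose of the rule is to avoid overestimating the time to worsening, and a reader could take that as a reason to move the event back to the last visit. The situation can also arise from the visit plan itself: ECOG is scheduled on Day 1 of each cycle and at end of treatment (Protocol 7.2.2.4), while survival is followed every 12 weeks after that (Protocol 4.1.5).

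At stake is the event indicator in the Kaplan-Meier estimates, median and quartiles of a named secondary endpoint. Every error of this kind would go one way, toward earlier apparent deterioration.

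**Working it through.** **Inputs**

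- Planned ECOG interval: 28 days (SAP 3.8.2.8, consistent with Protocol 7.2.2.4).
- Limit for counting a death as worsening: two planned intervals (SAP 3.8.2.8).
- Limit for patients with no post-baseline ECOG: 62 days (SAP 3.8.2.8).
- Randomized: 341 mutant and 231 non-mutant (Protocol, Amendment 5). I assume equal arms from the 1:1 ratio.

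**Limits**

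- Two intervals: 2 x 28 = 56 days. This number is not printed but follows directly.
- The SAP's 62 days is reproduced with visit windows added: 2 x 28 + 2 x 3 = 62.

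**The two examples under the rule**

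| Case | Gap | Against 56 days | Rule gives | Example says |
|---|---|---|---|---|
| Last ECOG week 6, death week 10 | (10 - 6) x 7 = 28 days | within | event at week 10 | deterioration at week 10 |
| Last ECOG week 6, death week 16 | (16 - 6) x 7 = 70 days | 14 days over | censored at week 6 | deterioration at week 6 |

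The second gap also exceeds 62 days, by 8 days, so the choice of limit does not matter. The time is week 6 either way; only the status differs.

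**Could the example be right in some other sense?**

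1. *Week 6 was already worsened.* Then the week-10 example, with the same last assessment, should also be dated at week 6. It is dated at death. The week-6 score is not given, so it is an inference that this visit was unworsened.
2. *The death is a backdated event.* The section's backdating rule uses the last assessment plus 28 days, which is week 10 and not week 6.
3. *The label just means the analysis time.* Then adjacent sentences use one label for opposite statuses, and status is exactly what the rule separates.

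None of these removes the conflict. The explicit rule, the cut-off rule and the questionnaire rule all point to censoring.

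**Size of one miscoded patient**

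Censoring leaves the Kaplan-Meier estimate unchanged at that time. A single untied event multiplies it, and every later value in that arm, by (1 - 1/n), where n is the number at risk. With a whole arm at risk:

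- Mutant: 341/2 = 170.5, so 1/171 to 1/170 = 0.58% to 0.59%.
- Non-mutant: 231/2 = 115.5, so 1/116 to 1/115 = 0.86% to 0.87%.

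The step grows as n falls. It is the size of one step, not an estimate of the shift in a median or in the contrast between arms.

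**The case against.** The best reply is that this is an editorial slip that the section already resolves. The rule is unambiguous and stands directly above the example. The example repeats the rule's trigger and its date, and an illustration does not override the rule it illustrates. The cut-off rule gives the same answer, because a death outside the limit does not count as worsening. The exact label occurs only in the two example sentences, and even the week-10 use is loose, since a death date is not an assessment date. Protocol 10.5.2.6 says nothing about death, so it does not settle the matter. Harm requires a programmer to prefer the example to the rule, and SAP Section 1 places the programming specifications in separate documents that are not available here. The number of affected patients cannot be determined, and those who start further anti-neoplastic therapy before worsening are already censored.

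Most of this stands, and it limits the point to a minor one: censoring is intended, no analysis decision is open, and no miscoding is shown. It does not make the example correct. The sentence sits in an operative event and censoring derivation and gives the wrong status for the case it describes. Because the specifications cannot be seen, the flag should be checked and not presumed right.

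**Conclusion.** The inconsistency is real. Under the SAP's own rule the week-16 death is censored at week 6, but the example words it as a deterioration at week 6. Only event status is affected, not the date.

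Severity is minor and the consequence is conditional on the example having been coded as written. It could touch only patients who had not worsened, had not been censored for further anti-neoplastic therapy, and died more than 56 days after their last ECOG. Their number is unknown. The per-patient step of about 0.6% or 0.9% rests on equal arms with everyone still at risk. The endpoint carries no test, so the primary and key secondary analyses are unaffected.

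**What to change.** In SAP Section 3.8.2.8, change the end of the second example so that it states that the patient is censored at week 6, in line with the rule and with the questionnaire rule in Section 3.8.2.9. Then confirm that the programming specifications, and any outputs already produced, set the event indicator for these deaths by the rule. The cost is a one-sentence correction and a check of one derived flag.
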